**FUNDING SOURCE**

This study is sponsored by Pfizer

Redacted

**4. AMENDMENTS AND UPDATES**

None

Redacted

## 5. MILESTONES

Milestone	Planned date
Completion of site selection	1 July 2016
Start of data collection (FSFV)	8 January 2017
End of data collection (LSLV)	31 January 2019
Study results	1 September 2019
Final study report	31 October 2019

## 6. RATIONALE AND BACKGROUND

Patients with chronic obstructive pulmonary disease (COPD) have been demonstrated to have an increased risk of pneumococcal disease. Pneumonia is frequent among patients hospitalized for COPD exacerbations and is associated with increased health care utilization and higher mortality. Nonpneumonic COPD exacerbations predict increased risk of subsequent exacerbations. Among community acquired pneumonia (CAP) patients with the highest severity of disease who require hospitalization, COPD is the most common comorbidity. These two diagnoses, CAP and acute exacerbations of COPD (AECOPD), come together when COPD patients acquire AECOPD caused by CAP.

Exacerbations are a significant component of the clinical course in COPD. Furthermore, as COPD progresses, exacerbations become more frequent. COPD exacerbations are defined as a complex of two or more respiratory symptoms (worsening dyspnea, cough, sputum production, chest tightness, or wheezing) related to the underlying COPD, with duration of 3 days or more, that require a change in treatment. Acute exacerbations of COPD (AECOPD) have a great impact on health status, disease progression, and prognosis. Up to 50%–70% of AECOPD can be attributed to respiratory infections by viruses or bacteria, even more in the most severe patients. They are often associated with the colonization of airways by multiple bacteria or viruses of low virulence that in normal conditions are parts of the normal flora of the upper airway.

Some studies have identified factors independently associated with bacterial growth, such as current smoking and *H. influenzae*; longer periods between exacerbations and *S. pneumoniae*; or decrease in FEV1 and *P. aeruginosa*. Traditionally, bacterial identification has been defined depending on the severity of the COPD, since *S. pneumoniae* and *M. catharralis*, are isolated in patients with predicted FEV1 >50%, and *H. influenzae*, Enterobacteriaceae and *P. aeruginosa* in those with FEV1 <50%.

Therefore, considering *S. pneumoniae* appears to be more frequent in patients with mild/moderate COPD, these subjects might be the most benefited from a preventive approach targeting this pathogen.

Redacted

In terms of costs, COPD represents a significant burden on the healthcare system. Different studies relate the costs to the severity or stage of the disease. The clinical course of COPD with multiple exacerbations has generated many economic studies analyzing these episodes. Anderson et al. in 2002, concluded that severe exacerbations represent 10 times the cost of a moderate exacerbation and around 60 times the cost of a mild-moderate episode. Similarly, exacerbations in severe COPD are 45 times more costly than in mild stages of the disease. The largest proportion of the cost of exacerbations is associated with hospitalizations, representing 65-85% of the total expense per acute episode.

All this evidence supports the current recommendations for immunization of patients with COPD with vaccines against influenza and *Streptococcus pneumoniae*, aimed to help prevent infectious exacerbations. Existing studies suggest an additive effect in the prevention of all-cause mortality with influenza and pneumococcal vaccines given together in elderly people, including in those with underlying chronic disease. Although no significant reduction in mortality rate was seen with the pneumococcal vaccine (PPV23) alone, there was a decrease in mortality rate of 27.0% (20.0–34.0) in subjects who received both vaccines compared to 16.0% (6.0–24.0) in those who received influenza vaccine. However, despite the existing recommendations these vaccines are generally under-used probably due to some persistent uncertainty about the benefits of vaccination.

There are two types of pneumococcal vaccines, a 23 valent polysaccharide vaccine and a 13 valent conjugate vaccine. The 23-valent pneumococcal polysaccharide vaccine (PPV23) is approved and recommended for use in persons  $\geq 2$  years of age for the prevention of pneumonia and pneumococcal disease. In the past decades many studies have evaluated the effect of PPV23 in adults, and effectiveness in preventing IPD has been reported, but with a short duration of protection, and limited impact on the total burden of disease even in countries with high uptake. Regarding the prevention of noninvasive pneumococcal pneumonia, the most common clinical presentation of the disease in adults, studies assessing the effectiveness of PPV23 show inconsistent results. Moreover, the available studies focused specifically on COPD patients, do not show a clear effect on any of the outcomes evaluated (developing pneumonia or acute exacerbations).

The 13 valent pneumococcal conjugate vaccine was approved by the EMA for the prevention of IPD in adults  $\geq 50$  in 2011, and subsequently in 2013 for adults  $\geq 18$  years of age, based on immunogenicity studies. Following the publication of the results of the CAPiTA study in 2015, showing the efficacy of the vaccine for the prevention of bacteremic (45.6%) and non-bacteremic (45%) pneumococcal pneumonia, and IPD (75%) caused by PCV13 serotypes in subjects  $\geq 65$  years old, the EMA approved the indication for the prevention of pneumonia in adults aged  $\geq 18$  years.

Recent exploratory studies have shown a beneficial effect of PCV13 in reducing the number of exacerbations in COPD and other respiratory diseases. Results from a group of 90 COPD patients vaccinated with PCV13 and followed for 2 years in Spain, showed a reduction of 50% in the number of severe exacerbations in the second year after immunization. A prospective comparative open label study carried out in Russia, evaluating PCV13 safety and effectiveness to prevent CAP in COPD patients compared with non-vaccinated patients, found in a group of 25 patients a 4.8-fold reduction in the incidence of exacerbations one year after vaccination.

The limitations of these preliminary results require larger studies, specifically designed for this purpose, to assess which sub-groups might benefit most from this preventive approach.

The aim of this study is to generate evidence to support vaccination of COPD patients with PCV13 and/or against influenza in terms of clinical benefits and also quality of life.

## 7. RESEARCH QUESTION AND OBJECTIVES

- **Primary objectives**

1. Evaluate the impact of routine clinical practice vaccination with PCV13 on the reduction of the risk of COPD moderate/severe exacerbations (see definitions) in adults, after 2 years of follow up.
2. Determine which subgroup of patients (based on the severity of COPD) benefit most from vaccination with PCV13  
COPD severity (GOLD)
  - GRADE 1: Mild/unknown [FEV1≤ 80%, FEV1/FVC < 0,7 or no spirometry data]
  - GRADE 2: Moderate [50% ≤ FEV1< 80%, FEV1/FVC < 0,7]
  - GRADE 3: Severe [30% ≤ FEV1 < 50%, FEV1/FVC < 0,7]
  - GRADE 4: Very severe [FEV1< 30% o FEV1< 50% plus respiratory failure, FEV1/FVC < 0,7])

- **Secondary objectives**

1. Evaluate the impact of influenza and PCV13 vaccination on the reduction of the risk of exacerbations
2. Evaluate the impact of vaccination with PCV13 on patients' quality of life
3. Evaluate the impact of vaccination with PCV13 on the decrease of FEV1
4. Estimate the potential economic savings for the healthcare system derived from vaccination of COPD patients with PCV13
5. Determine the prevalence of PCV13 vaccination in COPD patients.

## 8. RESEARCH METHODS

### 8.1. Study design

Prospective multicenter observational study, carried out in 6 different geographical areas in Spain (Salamanca, Cantabria, Palma de Mallorca, Madrid, Barcelona and Seville), involving 1 hospital in each region.

Redacted

The study would be carried out by a cohort study design: using subjects not vaccinated with PCV13 included in the study as a control group.

The specific number of patients to be included will be addressed in the analysis section depending on the recruited sample.

- Patients who do not receive PCV13 vaccination recommendation from their physicians
- Patients who, even after physician recommendation, they do not receive vaccination for different reasons
- Patients with some contraindications for vaccination with PCV13

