## **Study procedures**

Subjects identified with COPD will be informed about the study and invited to participate by investigators at the time of their routine control visits. All therapies will be prescribed according to the updated National COPD Guidelines (GesEPOC) indicating among other therapies active reduction of risk factors, influenza and pneumococcal vaccination (with PCV13) in all patients with mild, moderate or severe COPD. All the patients will be counselled to stop smoking and advised on life-style modifications. Any vaccination will be prescribed according to clinical practice and not related to the decision to include the subjects in the study. Subjects may be vaccinated before or after inclusion in the study.

Study will include periodic scheduled visits for all patients, to complete a total follow up of 2 years (see Table 1).

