### **8.2.2. Exclusion criteria**

Patients meeting any of the following criteria will not be included in the study:

1. Impossibility to perform prospective follow up
2. Present any immunocompromising condition
3. Present any other respiratory diseases as co-morbidity (subjects with overlap syndromes COPD-asthma will be excluded. Mixed phenotype defined as: symptoms of increased variability of airflow and incompletely reversible airflow obstruction)

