**TABLE 1. FOLLOW UP VISITS**

	Visit	0	1	2	3	4	5
	Month	0	1	6	12	18	24
Verification of inclusion/exclusion criteria		X	X	X	X	X	X
Informed consent signature		X					
Demographic variables		X					
Exacerbations and smoking history		X	X	X	X	X	X
Clinical history (hospital and/or primary care)		X					
Performance or verification of recent spirometry		X			X		X
Completion of QOL test		X			X		X
Treatment and vaccination recommendations adjustment (as per normal clinical practice)		X			X		X
Telephone Follow up (if applicable)				X		X	
PCV13 vaccination record			X		X		X
Influenza vaccination record			X		X		X
Updated treatment record			X		X		X

**Definitions:**

- COPD exacerbations are defined as a complex of two or more respiratory symptoms (worsening dyspnea, cough, sputum production, chest tightness, or wheezing) related to the underlying COPD, with duration of 3 days or more, that require a change in treatment.
  - *Treatment changes* include acute treatment with antibiotics and/or steroids, or an addition of new maintenance bronchodilator.
  - *Mild exacerbations* are those that require new prescription of bronchodilator only
  - *Moderate exacerbations* are those that require antibiotics and/or systemic corticosteroids without hospitalization,
  - *Severe exacerbations* are those that lead to hospitalization.
- The onset date of exacerbations is defined by the onset of the first recorded symptom.
- Exacerbations that occur within 7 days of onset of a prior exacerbation are counted as a single exacerbation

A subject presenting with exacerbation, will be considered as vaccinated at least 15 days after receiving immunization

Redacted

- Immunosuppression:
  - Lymphoma/Leukemia
  - Another neoplasm subjected to immunosuppressing treatments
  - Organ transplant with its corresponding immunosuppressing treatment
  - Leukopenia<1.000/mm; neutropenia<500/mm
  - Patients infected by Human Immunodeficiency Virus (HIV)
  - Congenital immunodeficiency
  - Diseases that requires continuous treatment with systemic corticosteroids administration for more than 14 days (prednisone at doses> 15 mg/day or other equivalent preparations), or cytotoxic agents during the previous six months.

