*Total proportion of subjects with FEV1 <40 should be less than 20% of the total study population (related to the microbiological etiology dependent on severity)^{14,15}

5.1.2 **Exclusion criteria**

Patients meeting any of the following criteria will not be included in the study:

1. *Impossibility to perform prospective follow up*
2. *Present any immunocompromising condition*
3. *Present any other respiratory disease as a comorbidity (subjects with overlap syndrome COPD-asthma will be excluded. Mixed phenotype defined as: symptoms of increased variability of airflow and incompletely reversible airflow obstruction)³³*

5.2 **SAFETY ANALYSIS**

NA

5.3 **OTHER ANALYSES**

NA

5.4 **SUBGROUPS**

The statistical analyses described in this SAP will be carried out according to the following analysis groups:

Exposed/unexposed (patients vaccinated/not vaccinated with PCV13):

The results will be evaluated through a cohort study, considering the subjects not vaccinated with PCV13 included in the study as the unexposed group.

COPD severity (GOLD):

- GRADE 1: Mild/unknown [$FEV1 \geq 80\%$, $FEV1/FVC < 0.7$ or no spirometry record]
- GRADE 2: Moderate [$50\% \leq FEV1 < 80\%$, $FEV1/FVC < 0.7$]
- GRADE 3: Severe [$30\% \leq FEV1 < 50\%$, $FEV1/FVC < 0.7$]
- GRADE 4: Very severe [$FEV1 < 30\%$ or $FEV1 < 50\%$ plus respiratory failure, $FEV1/FVC < 0.7$])

6 **OBJECTIVES AND VARIABLES**

Given that the primary objective of this study is to evaluate the impact of routine clinical practice vaccination with PCV13 on the reduction of the risk of moderate/severe COPD exacerbations, after 2 years of follow up, and to determine which subgroup of patients (based on the severity of COPD) benefit most from vaccination:

Primary endpoint to be analyzed:

- COPD severity (GOLD)¹⁸
 - GRADE 1: Mild/unknown [$FEV1 \geq 80\%$, $FEV1/FVC < 0.7$ or no spirometry record]
 - GRADE 2: Moderate [$50\% \leq FEV1 < 80\%$, $FEV1/FVC < 0.7$]

- GRADE 3: Severe [$30\% \leq \text{FEV1} < 50\%$, $\text{FEV1/FVC} < 0.7$]
- GRADE 4: Very severe [$\text{FEV1} < 30\%$ or $\text{FEV1} < 50\%$ plus respiratory failure, $\text{FEV1/FVC} < 0.7$])
- Number and severity of exacerbations
- Frequency of total exacerbations (moderate and severe) in previous years and during follow-up.

6.1 **OTHER OBJECTIVES**

For other study objectives, such as to determine the prevalence of PCV13 vaccination in COPD patients or to determine the impact of vaccination on quality of life or the decrease in FEV1:

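### The unexposed group pools contraindicated, not-recommended and recommended-but-unvaccinated patients, and no listed variable lets the analysis tell them apart

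*Protocol*

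**What the plan says.** Protocol 8.1 describes a cohort design "using subjects not vaccinated with PCV13 included in the study as a control group". Three bullets follow without a lead-in sentence: "Patients who do not receive PCV13 vaccination recommendation from their physicians"; "Patients who, even after physician recommendation, they do not receive vaccination for different reasons"; and "Patients with some contraindications for vaccination with PCV13". They can sensibly describe only the unvaccinated.

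The exclusion criteria (Protocol 8.2.2) cover impossible follow-up, other respiratory disease and immunocompromise ("Present any immunocompromising condition"). A contraindication to PCV13 is not among them.

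The variable list in Protocol 8.3 has pneumococcal vaccination, but not recommendation status, contraindication or reason for non-vaccination. Table 1 schedules a PCV13 vaccination record at months 1, 12 and 24. It shows recommendations only as a visit activity, at months 0, 12 and 24: "Treatment and vaccination recommendations adjustment (as per normal clinical practice".

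SAP 5.4 defines the comparator by "considering the subjects not vaccinated with PCV13 included in the study as the unexposed group". SAP 8.2.1 splits the exposed into four vaccine combinations, if numbers allow, and leaves the unexposed undivided.

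**The concern.** The exposed/unexposed contrast has a causal meaning only for patients who could have gone either way. A patient whose contraindication lasts through follow-up could not have been vaccinated, so no vaccinee matches that patient on this point. If the contraindication is also linked to exacerbation risk, including such patients distorts the control risk.

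The other two kinds reach the control group by different routes. Where the physician did not recommend the vaccine, confounding by indication is possible. Where the patient did not take it up, differences in health behaviour are possible. These can act in opposite directions, so the pooled figure may depend on the mix of kinds and may hide bias in each.

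Little else in the plan would reveal this. The exposed/unexposed tests of exacerbation rates in SAP 8.2.3.1 are unadjusted. The logistic models in SAP 8.1 and 8.2.3.1 list no covariate for reason. Both documents concede that the design gives no control over the named confounders. Comparing kinds of control is one of the few bias checks available, and it needs a variable that the plan does not list.

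**Working it through.** **Inputs from the documents.** Protocol 8.5 and SAP 5: 540 vaccinated and 1000 controls at enrolment; 378 and 700 at year 1; risks 27% and 37%; planned difference 10 percentage points; stated power 91.43%. SAP 4: significance level 0.05, taken here as two-sided.

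**Assumed inputs.** The share of each kind of control and its risk. The documents give neither.

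**1. Reproduce the stated power.** Two proportions, pooled variance under the null:
- pooled risk = (378×0.27 + 700×0.37)/1078 = 0.335
- SE0 = √[0.335×0.665×(1/378 + 1/700)] = 0.0301
- SE1 = √[0.27×0.73/378 + 0.37×0.63/700] = 0.0292
- power = Φ[(0.10 − 1.96×0.0301)/0.0292] = 91.9%, against 91.43% stated. It reproduces.

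**2. Shift from contraindicated controls alone.** Suppose the vaccine has no effect and everyone else has a 37% risk. With share c of controls contraindicated at risk q, the shift is c×(q − 37%). The last column is the chance that the 5% test rejects with 378 and 700 patients.

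| c | q | shift (points) | rejection rate |
|---|---|---|---|
| 5% | 47% | 0.5 | 5.3% |
| 5% | 57% | 1.0 | 6.2% |
| 10% | 47% | 1.0 | 6.2% |
| 10% | 57% | 2.0 | 9.8% |
| 20% | 57% | 4.0 | 24.8% |
| 10% | 27% | −1.0 | 6.3% |

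The last row shows that the sign reverses if contraindicated patients have the lower risk. For c of 5% to 10% with 10 to 20 points of excess, the shift is 0.5 to 2 points, or 5% to 20% of the planned 10-point effect.

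**3. What pooling can hide.** Again with no vaccine effect and assumed risks:
- Half the controls not recommended at 27%, half recommended but unvaccinated at 47%: 0.5×27 + 0.5×47 = 37%. Against vaccinees at 37%, the pooled contrast is 0, while the split contrasts are −10 and +10 points.
- Vaccinees at 35%; controls 70% recommended but unvaccinated at 40%, 25% not recommended at 30%, 5% contraindicated at 50%: 28 + 7.5 + 2.5 = 38.0%, a false benefit of 3.0 points. Without the contraindicated: (28 + 7.5)/0.95 = 37.4%, so 2.4 points remain. The split contrasts are +5 and −5 points.

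In the second example the contraindicated patients account for 0.6 of the 3.0 points. The mix of the other two kinds accounts for the rest.

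**4. Cost of removing contraindicated controls.** Formula of step 1, risks unchanged:
- 5% removed (665 left): 91.5%
- 10% removed (630 left): 90.9%
- 20% removed (560 left): 89.7%

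**The case against.** **The main impact tests do not use controls.** SAP 8.2.3.1 assesses the impact of PCV13 by paired before/after exacerbation rates in vaccinees, and does the same within severity grades. This stands. The point reaches only the exposed/unexposed tests and the logistic regressions.

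**The bias may not exist.** A contraindication that affects exposure alone and not exacerbation risk creates no confounding. The documents do not describe the contraindications, so neither the existence nor the direction of this bias is established. This stands, and it is why the size is given only under assumptions.

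**Routine-care controls are legitimate.** The objective concerns vaccination in routine practice, and all unvaccinated patients are one possible comparator. That is a reason to keep the all-unvaccinated contrast in the report, but not to leave its composition unexamined.

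**Excluding on later status could add bias.** A contraindication first recorded at month 12 or 24 may follow exacerbations. This stands, so the exclusion should use month 0 only.

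Three stronger readings are tempting but not supported:
- A reader might infer that contraindicated controls could never be vaccinated. Protocol 8.1 does not say that the contraindications are permanent, and Protocol 8.2 allows vaccination after inclusion.
- A reader might infer that the reason is not collected anywhere. The CRF (Annex 2) is not shown, so the documents establish only that no such variable is listed.
- A reader might see a contradiction between a not-recommended group and the guideline text in Protocol 8.2, "influenza and pneumococcal vaccination (with PCV13) in all patients with mild, moderate or severe COPD". That text does not name very severe disease, enrolment is open to any stage, and Protocol 9.5 leaves prescribing to the physician. Some patients without a recommendation are to be expected.

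**Conclusion.** The point holds as a cheap improvement to design and analysis. The plan pools three kinds of unvaccinated patient, removes none for contraindication, and lists no variable by which to separate them. The unadjusted exposed/unexposed tests and the logistic models are exposed to this.

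The size is unknown. For contraindicated patients alone it is probably modest: 0.5 to 2 points for shares of 5% to 10% with 10 to 20 points of excess risk, and large only if the share is large. Differences between the other two kinds could matter more and could cancel in the pooled figure. All shares and risks by kind are assumptions, and the calculations use the year-1 figures. The documents do not support a claim that the study's conclusion would be driven by the control mix, because the paired tests stand apart from it.

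**What to change.** **Protocol 8.3 and Table 1.** Add a month-0 item: PCV13 recommended, yes or no, and, if it is not given, one primary reason. State the order of precedence, because reasons overlap: contraindicated first, then not recommended, then recommended but not vaccinated. Record later changes for description only.

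**SAP 5.4.** Exclude patients contraindicated at baseline from the unexposed group in the exposed/unexposed contrasts and the logistic models. Keep the contrast against all unvaccinated patients as a sensitivity analysis. Pre-specify contrasts against not-recommended and against recommended-but-unvaccinated controls as bias checks, not as separate effect estimates, since each remains confounded.

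**Cost.** One eCRF field, at a visit where recommendations are already reviewed, and a few lines of SAP text. Some controls are lost: year-1 power is about 90.9% if 10% are removed, against 91.9% recomputed with none removed. The split contrasts are less precise. For example, at a 37% risk in both groups, the standard error √[0.37×0.63×(1/378 + 1/n)] rises from 3.1 points with n = 700 controls to 3.6 points with n = 350.

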## **8.2. Setting**

- This prospective non interventional study will be conducted by pulmonologists at hospital level. Regarding follow up or medical records, specialists may access clinical information from the Primary Care centers database related to the hospital.
- Periodic follow up of COPD patients is usually performed at ambulatory setting (may be at hospital or primary care centers). Commonly, databases containing clinical information for a patient are accessible from both settings, so data from previous years would be available to compare with data captured prospectively to the same standards.
- Recruitment will be performed in 6 hospitals in 6 geographical areas in Spain (Salamanca, Cantabria, Palma de Mallorca, Madrid, Barcelona, Seville).

